#### **4.15. Concomitant Medications**

Concomitant medications will be collected from the time of randomization through the end of the study. The medication name, start date, end date, and indication will be reported.

Special consideration should be given to report medications that may affect the healing process, such as:

- opioid medications (such as morphine)
- immunosuppressants
- corticosteroids
- non-steroidal anti-inflammatory drugs (NSAID)
- anticoagulant agents (such as heparin)

- all medications with a prophylactic indication
- all medications the Subject is given to treat an AE during the study

#### **4.16. Prohibited Procedures and Treatments**

Temporary coverage of the wound for the duration of the study with cell-based skin substitute products such as Apligraf® (Organogenesis), Dermagraft® (Advanced BioHealing), and cadaveric skin is prohibited. For patients in the Control group (collagenase ointment), ointment removal should be performed in a gentle manner and is not intended to be an aggressive mechanical debridement. For Subjects in both groups, no forms of mechanical debridement should be performed for the duration of the study.

#### **4.17. End of Study**

The following information will be documented:

- Last day of study participation
- Completion status – Did Subject complete the study (ie, 6-9 days of therapy)?
- Reason for study discontinuation

## 5. VISIT SCHEDULE AND DESCRIPTION OF STUDY VISITS

### 5.1. Schedule of Visits

Procedure Description	Visit 1 Screening Day -10 to 0	Visit 2 Randomization Day 0	Visit 3  Day 2-3	Visit 4  Day 4-6	Visit 5  End of Treatment Day 6-9	Unscheduled
Informed Consent	X					
Inclusion/Exclusion Criteria	X	X 				
Demographics and Subject Characteristics	X					
Medical and Surgical History	X	X 				
Laboratory Assessment for Pregnancy	X					
Wound Assessments	X	X 	X	X	X	X
Bedside Eschar Debridement (if needed)		X				
Initial Treatment Application		X				
Dressing Change			X 	X 		X 
Dressing Removal					X	X 
3D Imaging		X 	X	X	X	X
End of Study					X	X 
Concomitant Medication		X	X	X	X	X
Adverse Events		X	X	X	X	X

 Visit should not occur prior to 48 hours from the previous visit.

 Inclusion/Exclusion Criteria will be reconfirmed immediately prior to randomization if Visit 1 and Visit 2 are on different dates.

 If the screening visit and randomization occur on different days, the medical and surgical history will be updated (if changes have occurred).

 For patients undergoing eschar debridement prior to randomization, the procedure is performed before and after debridement (see Section 4.10).

 Dressing changes can occur daily for patients randomized to the collagenase ointment group (or more frequently if dressings become soiled).

 If the Subject is withdrawn early.

## 5.2. Description of Study Visits

### 5.2.1. *Visit 1/Screening/Days -10 to 0*

The following procedures and assessments will be performed and documented in the Subject's medical records/source notes:

- Informed consent
- Inclusion and exclusion criteria
- Demographics and Subject characteristics
- Medical and surgical history
- Laboratory assessment for pregnancy
- Wound assessment, including assessment of wound undermining

### 5.2.2. *Visit 2/Randomization/Day 0*

- Inclusion and exclusion criteria confirmation immediately prior to randomization
- Medical and surgical history update, if the Screening Visit and Randomization occur on different days.
- Wound assessment, including assessment of wound undermining (if the patient had eschar sharp and/or mechanical debridement prior to randomization refer to Section 4.10)
- Bedside eschar sharp and/or mechanical debridement (if needed) prior to randomization
- Initial treatment application
- Concomitant medications
- 3D imaging (if the patient had eschar sharp and/or mechanical debridement prior to randomization refer to Section 4.10)
- AE assessment and serious adverse event (SAE) reporting after randomization

### **5.2.3. Visit 3 and Visit 4/Follow-up Visits/Days 2-3 and Days 4-6**

Visits should not occur prior to 48 hours from the previous visit. The following procedures and assessments will be performed and documented in the Subject's medical records/source notes:

- Wound assessment
- Dressing change
- Concomitant medications
- 3D imaging
- AE assessment and serious adverse event (SAE) reporting

### **5.2.4. Follow-up Visits/Visit 5/End of Treatment/Days 6-9**

Visit should not occur prior to 48 hours from the previous visit. The following procedures and assessments will be performed and documented in the Subject's medical records/source notes:

- Wound assessment
- Dressing removal
- 3D imaging
- End of study
- Concomitant medications
- AE assessment and SAE reporting

### **5.2.5. Unscheduled Visits**

Outside of scheduled study visits, if the Subject needs to be assessed by the Investigator or a medically licensed sub-investigator for any reason, the following procedures and assessments will be performed and documented in the Subject's medical records/source notes:

- Wound assessment

- Dressing change
- Dressing removal, if Subject is withdrawn early
- 3D imaging
- End of study, if Subject is withdrawn early
- Concomitant medications
- AE assessment and SAE reporting

## 6. RISKS ASSOCIATED WITH STUDY PARTICIPATION

Participation in the clinical investigation presents low risks to Subjects. Some risks are generalized and are listed in Tables 2 and 3.

Table 2. Risks Associated With NPWTi-d/VFCC

Risks	Disorders/Conditions
Skin and Subcutaneous Tissue Reaction/Allergy	
 
• Skin rash, irritation, blistering
 
• Pruritus/itching
 
• Skin excoriation/breakdown/stripping
 
• Skin scarring if significant skin irritation were to occur
 
• Maceration
 
• Skin hyper/hypo-pigmentation at and/or around dressing application area
 
• Erythema/redness, edema, inflammation, or swelling at and/or around dressing application area
 

Mild Pain or Discomfort	
 
• Tenderness/minor ache at and/or around dressing application area
 
• Perspiration associated with wearing dressing
 
• Auditory irritation (due to a mild buzzing sound of negative pressure unit)
 
• Decreased sleep or sleep quality
 
• Paresthesia (numbness, tingling, prickling, creeping sensation)
 
• Pain upon dressing removal
 

Other	
 
• Bleeding
 
• Localized infection
 
• Autonomic dysreflexia (in Subjects with spinal cord injury)
 
• Retained foreign debris (eg, foam) in the wound
 
• Impairment of mobility/activity (limitation secondary to weight and attachment of therapy unit)
 
• Possible tubing entanglement/trip or slip hazard leading to fracture, tissue damage
 
• Stalled healing/non-progression of healing
 
• Deterioration of the wound
 
• Systemic reaction (due to an allergic reaction to dressing materials)
 

**Table 3: Risks Associated with collagenase ointment**

Risks	Disorders/Conditions
Skin and Subcutaneous Tissue Reaction/Allergy	
 
Collagenase ointment is contraindicated in patients who have shown local or systemic hypersensitivity to collagenase.
 
A slight transient erythema has been noted occasionally in the surrounding tissue, particularly when collagenase ointment was not confined to the wound.
 
Pain or burning sensation in the wound
 

Other	
 
The optimal pH range of collagenase is six (6) to eight (8). Higher or lower pH conditions will decrease the enzyme's activity and appropriate precautions should be taken.
 
The enzymatic activity is adversely affected by certain detergents and heavy metal ions such as mercury and silver, which are used in some antiseptics.
 
Debilitated patients should be closely monitored for systemic bacterial infections because of the theoretical possibility that debriding enzymes may increase the risk of bacteremia.
 

## 7. SAFETY AND ADVERSE EVENTS

### 7.1. Definitions

#### 7.1.1. *Adverse Event (AE)*

Any untoward medical occurrence, unintended disease or injury, or untoward clinical signs (including clinically significant abnormal laboratory findings) in Subjects, users or other persons, whether or not related to the investigational medical device.

[figure not shown]
#### 7.1.2. *Serious Adverse Event (SAE)*

An AE is considered serious if it results in any of the following outcomes:

- Death
- Life-threatening
- Hospitalization (initial or prolonged)
- Persistent or significant incapacity or substantial disruption of the ability to conduct normal life functions
- Congenital anomaly/birth defect

- Required intervention to prevent permanent impairment or damage
- Other important medical events may be considered serious when, based upon appropriate medical judgment, they may jeopardize the Subject and may require medical or surgical intervention to prevent one of the outcomes listed in this definition.

## 7.2. Classification

### 7.2.1. Relationship to Study Treatment

The Investigator will assess the relationship of the AE as:

- **Related** to the study product: any AE for which there is a reasonable possibility that the study product caused the AE. The Sponsor will review all SAEs for expectedness.
- **Not Related** to the study product: when it is determined that there is no relationship between the AE and the use of the study product.

### 7.2.2. Severity

The Investigator will assign severity as:

- **Mild** – asymptomatic or mild symptoms; clinical or diagnostic observations only; no intervention indicated
- **Moderate** – minimal, local, or non-invasive intervention indicated

- **Severe** – medically significant but not immediately life-threatening; hospitalization or prolongation of hospitalization indicated; disabling

### 7.3. AE Reporting Procedures

The Investigator is responsible for monitoring the safety of all Subjects enrolled in the study and reporting AEs as described in this protocol.

### 7.4. AE Collection/Reporting Period

The AE collection/reporting period will begin after the Subject has been randomized. Investigators should assess for AEs at each visit. In addition, study Subjects should be instructed to report any AE that they experience to the Investigator.

All AEs, regardless of perceived relationship to study product, will be reported and recorded on the appropriate case report forms (CRFs) in a timely manner. In addition, the worsening of a medical condition previously reported in the medical history should also be recorded as an AE.

The AE description will include the nature of the experience (AE term), the start date, the end date, the severity of each sign or symptom, the seriousness of the event or experience, relationship to study treatment, the course of action taken, and the outcome of the experience. It will be indicated if the AE caused the Subject to be discontinued from the study.

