## 4. STUDY PROCEDURES AND ASSESSMENTS

### 4.1. Informed Consent

The Investigator, or designee, will discuss the purpose of this study with potential Subjects or their legally authorized representative if the Subject is unable to provide their own informed consent. Each individual will review the Informed Consent Form (ICF) approved by the local Institutional Review Board (IRB). The ICF must be signed according to IRB requirements before the Subject can undergo any study-related procedures. Informed consent will be obtained under these conditions:

- Subjects or their legally authorized representatives must be made aware of the purpose of the study and the potential risks and benefits known or that can be reasonably predicted or expected.
- Subjects or their legally authorized representatives must be given the opportunity to ask the Investigator questions and must be provided time to consider participation in the study.
- ICFs will be written in a manner that is non-technical and understandable to the Subject or their legally authorized representative.
- Subjects or their legally authorized representatives will not be led to believe that they are waiving their legal rights to release the Investigator, KCI®, the study site, or any of their agents from liability for negligence.
- Subjects or their legally authorized representatives will be asked to sign and date the ICF indicating their informed consent to participate in the study.
- The Investigator's responsibilities during the ICF process include:

- screening out potential Subjects who may not be able or willing to comply with the study protocol.
- ensuring that Subjects or their legally authorized representatives have signed the ICF prior to undergoing any study-related assessments.
- ensuring that each Subject or their legally authorized representative receives a copy of the signed ICF.

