### **4.2.1. *Inclusion Criteria***

The Subject:

1. is anticipated to be hospitalized for the duration of treatment (minimum of 6 days).
2. is  $\geq 18$  years of age.
3. or their legally authorized representative is able to provide informed consent.
4. has been diagnosed with a wound (eg, chronic, acute, traumatic, or dehisced wounds) and/or ulcer (ie, full-thickness wounds) that meets the following criteria:
  - a) total surface area measuring  $\geq 16 \text{ cm}^2$ , including a minimum width of 2 cm (before removal of eschar at the bedside and excluding undermining).
  - b)  $< 20 \text{ cm}$  across (edge-to-edge) at any point perpendicular to the wound edges.
5. has, in the opinion of the investigator, no more than 2/3 of the wound bed surface area considered to be clean, healthy, and viable. If eschar is present at baseline, it must be removed by bedside debridement prior to assessing the percentage of

clean, healthy, and viable wound bed.

6. has a negative urine or serum pregnancy test at screening (if female and has potential for pregnancy) and is willing to take precautionary measures to prevent pregnancy during the duration of the study (up to 9 days).

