#### **4.2.2. *Exclusion Criteria***

The Subject:

1. has been diagnosed with malignancy in the wound.
2. has untreated osteomyelitis.
3. has an untreated systemic infection.
4. has active cellulitis in the periwound area.
5. has a known allergy or hypersensitivity to study materials: collagenase ointment, dressing(s), and/or dressing components such as acrylic adhesives or polyurethane.
6. has, in the opinion of the investigator, a clinically significant condition that would impair the Subject's ability to comply with the study procedures.
7. has had radiation directly to the wound area.
8. has been diagnosed with a major vascular deficit limiting arterial inflow to the wound region, as determined by the Investigator's interpretation of the Subject's medical history.
9. has eschar in the wound that cannot be removed by bedside sharp and/or mechanical debridement.
10. is participating in another interventional clinical trial for the duration of the study.
11. has unexplored fistulas in the wound or fistulas in the wound that connect to other body cavities.
12. has a wound with any tunneling present.

13. has inadequate hemostasis at the wound site, as determined by the investigator.

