#### **4.10. Bedside Eschar Debridement**

Bedside sharp and/or mechanical debridement procedures will be allowed before randomization to remove eschar. However, sharp or mechanical debridement of the study wound after randomization is not permitted. For those Subjects having bedside sharp and/or mechanical debridement prior to randomization, there will be two wound assessments prior to initiation of treatment.

- 1) Prior to debridement, the investigator or a medically licensed sub-investigator, or a practitioner working under the licensure of the Investigator or sub-investigator, will measure the wound to confirm that the wound size matches inclusion criteria #4 in Section 4.2.1. In addition, a three-dimensional (3D) image of the wound will be taken prior to debridement.
- 2) After debridement, the investigator will assess the wound to confirm the wound has no more than 2/3 viable tissue. In addition, a 3D image of the wound will be taken after debridement. This 3D image will be used for the baseline measurement that subsequent images are compared to for any changes in size/tissue composition.

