### 7.5. SAE Reporting to KCI®

The SAE collection/reporting period will begin after the Subject has been randomized. SAEs will be reported via the KCI® SAE Report Form. This form should be completed by the Investigator, or designee, and submitted (fax or email) to KCI® within 24 hours of the Investigator becoming aware of the event. The KCI® SAE inbox is available for SAE reporting 24 hours per day and is monitored during normal business hours.

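### AE and SAE collection opens only after randomisation, so harms from the pre-randomisation eschar debridement that start before randomisation, or occur in debrided screen failures, have no reporting route to the sponsor

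*Protocol*

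**What the plan says.** Three places in the protocol set the start of safety collection, and they agree. Section 7.4: "The AE collection/reporting period will begin after the Subject has been randomized". Section 7.5: "The SAE collection/reporting period will begin after the Subject has been randomized". The Day 0 list in section 5.2.2: "AE assessment and serious adverse event (SAE) reporting after randomization".

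The debridement comes earlier. Inclusion criterion 5 (section 4.2.1) says: "If eschar is present at baseline, it must be removed by bedside debridement prior to assessing the percentage of" viable wound bed. The Day 0 list has "Bedside eschar sharp and/or mechanical debridement (if needed) prior to randomization", and the schedule in section 5.1 shows it as a Visit 2 procedure. Section 4.10 uses softer wording: "Bedside sharp and/or mechanical debridement procedures will be allowed before randomization to remove eschar". Consent precedes all of this; section 4.1 says "The ICF must be signed according to IRB requirements before the Subject can undergo any study-related procedures".

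Subjects who fail eligibility are screen failures and are not randomised (sections 4.2 and 4.8). One exclusion that can apply after debridement is criterion 13: the subject "has inadequate hemostasis at the wound site, as determined by the investigator".

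**The concern.** The debridement is sharp or mechanical, is scheduled by the protocol, and is what allows a subject with eschar to be assessed for eligibility. It takes place after consent, when the subject is already in the study, but before the point at which the sponsor starts to receive safety information.

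Take a consented subject whose eschar is debrided on Day 0 and whose wound then bleeds enough for the investigator to apply exclusion 13. That subject is never randomised, so collection under sections 7.4 and 7.5 never opens. The bleed has no AE form, and if it is serious it has no 24-hour SAE report. Subjects harmed by the procedure are among those most likely to leave the study before collection begins.

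What is at stake is subject protection and complete reporting of harms from a study procedure. No efficacy or comparative safety result is at stake.

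**Working it through.** The point needs no arithmetic, and the plan states no figure to reproduce. The check is the order of events and a search for any other route that would carry a harm to the sponsor.

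**Order of events**

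1. Consent is signed (Protocol 4.1).
2. Screening takes place, Day -10 to Day 0 (5.2.1).
3. If eschar is present, bedside debridement is done at Visit 2, Day 0 (4.2.1, 4.10, 5.1, 5.2.2).
4. After debridement the investigator checks that no more than 2/3 of the wound bed is viable (4.10).
5. The subject is randomised, and AE and SAE collection opens (7.4, 7.5).
6. Study treatment is first applied, and the treatment-emergent period opens (Protocol 8.1.3; SAP 9.2).

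The uncovered interval runs from step 3 to step 5.

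**Debridement harms by time of onset**

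- *Before randomisation, subject later randomised:* not collected as an AE or SAE.
- *Any time, subject debrided and then screen-fails:* not collected, because step 5 never happens.
- *After randomisation:* collected, because section 7.4 records all AEs whatever their suspected cause.

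**Ways to screen-fail after debridement**

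- Exclusion 13, inadequate hemostasis.
- Exclusion 9, eschar that bedside debridement cannot remove. This may become clear only on trying.
- The post-debridement check in section 4.10, if more than 2/3 of the bed then proves viable.

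**Other routes considered**

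- *Medical history:* updated at Visit 2 only if screening and randomisation fall on different days (4.6). It is not a safety report. Later worsening of a recorded condition would count as an AE (7.4).
- *Concomitant medications:* collected from randomisation (4.15), so treatment given for an earlier event need not appear.
- *Disposition tables:* give the reason for screen failure (Protocol 8.3.2; SAP 7.1), but are not specified to give an event term, severity, seriousness or outcome.
- *Wound assessment and 3D imaging before and after debridement* (4.10): document the wound. They are not event reports.
- *Unanticipated device effects* (7.6): the sponsor evaluates the SAEs it has received, so an SAE outside the collection period does not reach this step.
- *Causality* (7.2.1): judged only against the study product, so there is no category for a debridement harm even when it is recorded.
- *Follow-up* (7.7): the 30-day follow-up covers treatment-related events only. Unrelated events close when participation ends.
- *Date conventions* (SAP 6.3.2): an event with a missing start date that ended before first application is treated as pre-study and left out of summaries.

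None of these gives an AE or SAE route for the interval from step 3 to step 5.

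**The case against.** The strongest reply is that the start of collection is a deliberate choice, applied consistently in sections 5.2.2, 7.4 and 7.5, so the protocol does not contradict itself. Debridement is not the study product. It is needed only when eschar is present, and section 4.10 describes it as permitted. For randomised subjects the uncovered interval is part of one visit. The missed events precede allocation and first application, so they cannot affect the between-arm comparison. All of this stands. It limits the reach of the point, but it gives no reporting route to a serious event in the interval.

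Some stronger readings are tempting, and the documents do not support them:

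- A reader might infer that debridement harms are never recorded. Later bleeding or infection with onset after randomisation is recordable under section 7.4.
- A reader might infer that the step would look free of events whatever happened. Screen-failure reasons are tabulated, so an exclusion for hemostasis would be visible as a reason, though not as an event.
- A reader might infer that IRBs could not learn of such harms. Section 7.5 governs reporting to the sponsor. What an investigator owes the IRB depends on requirements not reproduced in these documents, and section 7.3 keeps the investigator responsible for monitoring the safety of all enrolled subjects.
- A reader might infer that an event ongoing at randomisation becomes baseline history. The documents do not say how such an event is classified.

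It is also fair to say that opening SAE reporting at consent could bring in up to 10 days of unrelated inpatient events. The fix below therefore starts at the debridement.

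**Conclusion.** The point holds in a limited form. Debridement harms with onset before randomisation, and harms in subjects who are debrided and then screen-fail, have no AE or SAE reporting route to the sponsor. Followed as written, the protocol would leave a serious harm from a scheduled invasive procedure outside the 24-hour report.

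The size cannot be stated. The documents do not give the number of subjects with eschar, the number debrided or the complication rate. For a randomised subject the gap lasts from debridement to randomisation within Day 0. For a debrided screen failure it covers everything that follows. Treatment-emergent counts and the between-arm safety comparison do not change.

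The conclusion assumes that debridement is done at Visit 2 after consent, as scheduled, and that no site or IRB procedure outside these documents sends the events to the sponsor. The change should be made because it improves subject protection at low cost. It is not needed to protect the trial's inference.

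**What to change.** - **Protocol 7.4, 7.5 and the Day 0 safety line in 5.2.2:** start reporting of SAEs, and of AEs judged related to the bedside debridement, when that debridement begins. State that this includes subjects who then screen-fail.
- **Protocol 7.2.1:** add a causality category for events related to the study procedure (debridement).
- **Protocol 7.7:** extend the follow-up of ongoing events to these events.
- **SAP 9.2:** add a separate listing of pre-treatment events. Base it on all debrided subjects, because screen failures are outside the Safety Analysis Set (SAP 5.1). Make clear that the pre-study rule in SAP 6.3.2 does not remove events from this listing.
- **Leave unchanged:** the treatment-emergent definition and all comparative tables.

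The cost is protocol and SAP wording, one added causality option on the existing forms, and a small amount of safety reporting on some screen failures. The volume cannot be estimated, because the number debrided is not given. No clinical rule changes.
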